19.2 Statistical methodology and assumptions

19.2.1 Summary statistics for continuous data

Summary statistics (including N, mean, standard deviation, minimum, lower quartile, median, upper quartile, maximum) will be provided for continuous data by visit and treatment group.

19.2.2 Analysis of covariance

Endpoints with continuous data type expected to be normally distributed (change from baseline) will be analyzed using a mixed-effects repeated measures model (MMRM). The explanatory variables will be weight, TNF α status, analysis visit, analysis visit by baseline score and baseline score. Since the MMRM will be applied only to the originally randomized AIN457 150 mg group the treatment factor will not be included in the model. An unstructured correlation matrix will be used thus allowing adjustment for correlations between time points within subjects.

SAS code for mixed model:

```
proc mixed data=<aaa>;
class TRT USUBJID AVISITN;
model CHG= WEIGHT TNF $\alpha$  AVISITN BASE BASE*AVISITN / s ddfm=kr;
lsmeans AVISITN / cl;
repeated AVISITN / type=un subject=USUBJID;
Run;
```

In case the MMRM model does not converge the following sequential steps will be used:

1. change ddfm=kr to ddfm=bw. If still no convergence, perform step 2.
2. change type=un to type=cs. If still no convergence, perform step 3.
3. remove covariates BASE*AVISITN.

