5.1 Analysis Sets

The following analysis sets will be used for the data analysis:

Extension Full Analysis Set (extension FAS): The extension FAS will be comprised of all subjects enrolled in the extension study.

(In this document extension FAS is referred to as FAS).

Of note, FAS will comprise only the subjects from extension whereas safety set will include from core or extension, safety set will be larger than FAS.

Up-titration Subset: The up-titration subset will be comprised of all subjects from the extension FAS set who received at least one dose of the up-titration dose.

[REDACTED]

Safety set: The safety set includes all subjects enrolled in the core study who took at least 1 dose of study treatment during the core study. Subjects will be evaluated according to treatment received.

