5.2 Treatment groups

Unless otherwise specified, the summaries will be performed by the treatment sequence.

- Efficacy:

- AIN457 10 mg/kg - 75 mg -150 mg
- AIN457 10 mg/kg - 150 mg
- Placebo - AIN457 75 mg – 150 mg
- Placebo - AIN457 150 mg
- Any AIN457 75 mg
- Any AIN457 150 mg

After week 52 the combination of assigned treatments will also be shown as follows:

- AIN457 75 mg & Placebo - AIN457 75 mg
- AIN457 150 mg & Placebo - AIN457 150 mg

Tables on MMRM or MI estimates will be summarized only for the AIN457 10 mg/kg - 150 mg originally randomized group.

- Safety
 - Any AIN457 75 mg
 - Any AIN457 150 mg
 - Any AIN457

Placebo treatment group will be displayed only in safety listings and in in-tex safety tables.

6 Subgroup definitions

The primary endpoint(s) and secondary endpoints will be evaluated by TNF-alpha inhibitor status.

7 Assessment windows, baseline and post baseline definitions, missing data handling

Baseline and post-baseline definitions

In general [REDACTED], a *baseline* value refers to the last measurement made prior to administration of the first dose of study treatment. A post-baseline value refers to a measurement taken after the first dose of study treatment.

For X-ray, a baseline value is the last measurement prior to dosing if available, or the first value within 30 days post dosing if no other value is available prior to dosing.

[REDACTED]

For post baseline visit -windows during the core study the following applies (unless otherwise specified):

For quantitative variables, the closest to the actual visit is chosen (if two assessment have the same distance, then the earlier now will be chosen)/

For qualitative variables, the worst record is selected. It is noted that in the analysis performed, worst case is always well defined (e.g., for urine protein values “+” and “++” the worse case is defined as “++”).

Analysis visit windows

Analysis visit windows will be used for the data that is summarized by visit; they are based on the study evaluation schedule and comprise a set of days around the nominal visit day. For any assessment, there are protocol defined scheduled visits around which analysis visit windows were created to cover the complete range of days within the study. The analysis visit windows and rules for dealing with multiple measurements within the windows are described in [Section 19.1](#).

For visits that occur after week 104, the recorded nominal visit data will be considered.

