12.3 Handling of missing data

Missing data

Analysis of study data will be based on the observed data. In addition to the observed data approach, multiple imputation technique will be employed for the following binary variables: ASAS20, ASAS40, [REDACTED]

[REDACTED] Analysis will be limited to the higher originally randomized dose (AIN457 10 mg/kg - 150 mg)

For analyses of these parameters, if all post baseline values are missing then these missing values will not be imputed and this subject will be removed from the analysis of the corresponding variable, i.e. it might be that the number of subjects providing data to an analysis is smaller than the number of subjects in the FAS.

[REDACTED] mixed model repeated measures (MMRM) will be fitted assuming random missingness to assess the durability of secukinumab effect. The explanatory variables will be baseline score, weight,

TNF α status, analysis visit, and analysis visit by baseline score. An unstructured correlation matrix will be used thus allowing adjustment for correlations between time points within subjects. This analysis will be done on the entire treatment period for the AIN457 10 mg/kg - 150 mg treatment arm.

13 Analysis of the primary variable(s)

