16.6 Compound specific safety evaluation

Safety topics of interest, such as risks defined in the Safety Profiling Plan, Risk Management Plan or topics of interest regarding signal detection or routine analysis are defined in the Program Case Retrieval Sheet that is stored in CREDI at the path *Cabinets/CREDI Projects/A/AIN457A/Integrated Medical Safety*.

The crude incidence and exposure-adjusted incidence rates will be summarized. In addition, listings will be provided presenting which subjects experienced which risk.

Important note: For the evaluation of SPP risks primary and secondary system organ classes of the MedDRA dictionary (latest version) will be considered.

17 Interim analyses

Interim analyses are planned in order to support regulatory filing and for purpose of publication after subjects complete additional years of treatment in this extension study. Additional analyses may be performed to support health authority interactions, as necessary.

18 Determination of sample size

It is estimated that approximately 75% to 85% of subjects enrolled in the core study will complete the entire treatment period and be eligible for entry into the extension study, which is equivalent to about 279 to 316 subjects.

19 Appendix

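### If the unstructured MMRM fails to converge, the SAP falls straight to compound symmetry with model-based standard errors; Week 260 intervals are then too narrow if variance grows over time

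*SAP*

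**What the plan says.** SAP 19.2.2 models change from baseline with weight, TNF status, visit, baseline and baseline-by-visit, using `type=un`, `ddfm=kr` and no EMPIRICAL option, so standard errors are model-based. It is a one-arm model: "Since the MMRM will be applied only to the originally randomized AIN457 150 mg group the treatment factor will not be included". SAP 12.3 fixes the span and gives the purpose as durability of effect: "This analysis will be done on the entire treatment period for the AIN457 10 mg/kg - 150 mg treatment arm".

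If the model does not converge, there are three steps:

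1. "change ddfm=kr to ddfm=bw. If still no convergence, perform step 2"
2. "change type=un to type=cs. If still no convergence, perform step 3"
3. Drop the baseline-by-visit term.

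No structure lies between unstructured and compound symmetry, and nothing requires the report to state which one was used. SAP section 2 applies the model to the continuous variables of the hierarchy; the endpoint names in 12.3 are redacted. SAP section 4 labels all p-values and confidence intervals exploratory.

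**The concern.** An unstructured matrix across five years asks for many parameters from one arm, so the fallback deserves the same care as the main model. Step 1 acts after the REML fit: it changes the degrees of freedom and removes the Kenward-Roger adjustment, but the likelihood and covariance estimate stay as they were. It therefore cannot cure a covariance fit that has not converged. In effect the covariance goes in one move to two parameters: one variance for every visit and one correlation for every pair of visits.

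If the variance of change grows with time, the pooled variance understates the late visits, and the model-based interval at Week 260, where durability is judged, is too narrow. A reader of the report would not know that this structure had been used.

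**Working it through.** **Sample size as stated.** SAP section 18 expects "approximately 75% to 85% of subjects enrolled in the core study" to enter the extension, "which is equivalent to about 279 to 316 subjects". Back-solving gives 279/0.75 = 372.0 and 316/0.85 = 371.8. With a core N of 371 (not stated), 0.75 × 371 = 278.25 and 0.85 × 371 = 315.35, which round up to 279 and 316. The figure is reproduced.

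**Arm size.** Efficacy uses extension enrollees only (SAP 5.1: "The extension FAS will be comprised of all subjects enrolled in the extension study"). SAP 5.2 implies three core groups: 10 mg/kg then 75 mg, 10 mg/kg then 150 mg, and placebo. The ratio is not stated. Assuming 1:1:1, 279/3 = 93 and 316/3 = 105. Shares of 25% to 40% would give about 70 (0.25 × 279) to 126 (0.40 × 316).

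**Visits.** Protocol Tables 6-1 to 6-3 schedule 12 efficacy visits: Weeks 116, 128, 140, 156, 168, 180, 192, 208, 220, 232, 244 and 260. Adding only the core time points named in the documents (Weeks 1, 16, 52 and 104) gives 16. Protocol 3.1 calls Week 16 Visit 8, so the core count is probably higher; up to 30 in total is an assumed upper end.

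**Unstructured parameters, T(T+1)/2.** 12 visits: 78. 16: 136. 25: 325. 30: 465. Against 93 to 105 subjects, that is 0.74 to 0.84 per subject at 12 visits and 4.4 to 5.0 at 30. Compound symmetry has 2.

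**Does the unstructured fit fail?** Two sets of simplified REML fits were run with a 50-iteration limit; neither is PROC MIXED.

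- Fisher scoring with step-halving, SD rising from 1.8 to 2.6 and 20% or 33% dropout: 120 of 120 converged at 12 visits, 24 of 24 at 26 visits, 3 of 3 at 30 visits.
- A Newton fit: 16 of 16 converged at 12 to 16 visits, but only 1 of 3 at 26 visits.

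Failure is thus unlikely at 12 to 16 visits. At 25 or more the runs are few and depend on the algorithm.

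**Complete-data check of compound symmetry.** The model gives each visit the average variance, so model SE / true SE at the last visit = √(mean of visit variances) / SD at the last visit. For an SD rising linearly from 1 to r, the mean variance is about (1 + r + r²)/3.

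- r = 1.25: √1.271 / 1.25 = 0.90; coverage 2Φ(1.96 × 0.902) − 1 = 92.3%.
- r = 1.5: √1.583 / 1.5 = 0.84; coverage 90.0%.

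**Simulation with dropout.** Compound-symmetry REML with the SAP mean model, n = 93 or 105, 13 or 25 visits, 20% extension dropout, correlation decaying with time, 1,000 runs per scenario, z = 1.96. Monte Carlo error is about 0.7 to 1.1 points.

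| SD, last/first | Model SE / true SE | Coverage, model SE | Coverage, sandwich SE |
|---|---|---|---|
| 1.0 | 0.94–0.99 | 92.2–95.4% | 93.3–95.7% |
| 1.25 | 0.82–0.88 | 88.7–90.8% | 93.0–94.7% |
| 1.5 | 0.76–0.80 | 86.4–88.5% | 92.9–94.6% |
| 0.8 (n = 93, 25 visits only) | 1.08 | 96.0% | 93.5% |

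With dropout that depends on observed values (MAR), r = 1.25, n = 93 and 25 visits, coverage was 89.5% (sandwich 93.9%) and the bias in the mean was −0.03 first-visit SD. For an SD rising from 1.8 to 2.6, a separate check gave a model SE of 0.23 to 0.24 against a true 0.30 to 0.31, with coverage of 87% to 88% (sandwich 93% to 94%). A smaller simulation with that rise (300 runs per scenario, about 33% missing at the last visit) gave 82% to 86%. The conclusion rests on the 1,000-run figures.

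**The case against.** The strongest reply is that the fallback may never be used. A parameter count does not show non-convergence, because each subject contributes many correlated observations, and most of the trial fits converged. A reader might infer from 78 to 465 parameters that failure is to be expected. The documents do not support that: they do not give the number of modelled visits, and the fits point the other way at 12 to 16 visits. This part of the objection stands.

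A reader might also infer that late intervals will be too narrow. That needs rising variance, and the documents give no SD by visit. The direction of error is unknown until the data are seen. This stands too.

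Third, little hangs on the model. It is exploratory and single-arm, and ASAS20 and ASAS40 are summarised from observed data (SAP 12.3 and 14.1). SAP 14.1 and 19.2.1 also give change from baseline with N, mean and SD by visit, so a reader can see whether the spread grows and can compute a standard error free of compound symmetry. This limits the severity, but it does not make the model-based interval right.

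Fourth, Kenward-Roger adds computation after the fit, so step 1 might rescue a run that fails only there. That is possible, but it is a different failure from non-convergence of the covariance, which is what the ladder is written for.

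**Conclusion.** The point holds conditionally and is minor. If the unstructured fit fails, step 1 cannot repair it, and step 2 gives Week 260 intervals that cover about 86% to 91% when the SD of change rises 1.25- to 1.5-fold, against about 93% to 95% with a sandwich standard error. With constant SD the loss is small. With falling SD the interval is too wide.

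Arm size (1:1:1 allocation), total visits, dropout and SD pattern are all assumptions. A reader might go further and infer that the durability estimate itself is seriously biased; the one MAR scenario showed only −0.03 SD, so the issue is the standard error. Nor is the primary ASAS20 summary touched. This is a cheap improvement to an exploratory analysis.

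**What to change.** In SAP 19.2.2:

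- Replace step 1 with an ordered list of heterogeneous structures, for example TOEPH, then ARH(1), then CSH, before compound symmetry.
- For any structure other than unstructured, use the EMPIRICAL (sandwich) standard error with between-within degrees of freedom.
- List the visits in the model, and report the structure used for each endpoint.
- If the switch from `kr` to `bw` is wanted for runs where the covariance fit converges and only the Kenward-Roger step fails, say so separately.

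The cost is a few lines of SAP text and one SAS option. Late-visit intervals may be somewhat wider. Where compound symmetry was exactly true, the sandwich interval covered about one point less than the model-based one (93.6% against 94.6% with complete data, 94.3% against 95.3% with dropout). The sandwich standard error corrects the interval width, not any bias in the mean.

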19.2.3 Summary statistics for binary and categorical data

Summary statistics for discrete variables will be presented in contingency tables and will include count and frequency in each category. If applicable, CIs will be derived as well based on the score method including continuity correction ([Newcombe 1998](#)):

With z as (1-alpha/2)-quantile of the standard normal distribution (SAS: $z=PROBIT(1-\alpha/2)$), n as total number of subjects (i.e. number of subjects in the denominator), and p as estimated crude incidence (number of subjects with event / n) it is $q=1-p$

Then the lower limit is

$$L = 100 \times \max \left(0, \frac{2np + z^2 - 1 - z\sqrt{z^2 - 2 - \frac{1}{n} + 4p(nq+1)}}{2(n+z^2)} \right)$$

and the upper limit is

$$U = 100 \times \min \left(1, \frac{2np + z^2 + 1 + z\sqrt{z^2 + 2 - \frac{1}{n} + 4p(nq-1)}}{2(n+z^2)} \right).$$

In addition, if $L > p$ then $L = p$ and if $U < p$ then $U = p$.

If appropriate, an exact $100*(1-\alpha)\%$ CI ([Clopper-Pearson 1934](#)) will be obtained by using the SAS procedure PROC FREQ with the EXACT BINOMIAL statement. However, the CI derived via the score method including continuity correction will be the default in safety analyses.

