3.2 Secondary objectives

1. To evaluate the sustainability of subject benefits in subjects with active AS as quantified by the ASAS40 response during long-term treatment with secukinumab 75 or 150 mg.
2. To evaluate the overall safety and tolerability of secukinumab in subjects with active AS.

4 Data presentation

Data analyses will be presented by treatment groups. For efficacy analysis the assigned and actual treatment will be displayed.

Unless otherwise stated, summary tables/figures/listings will be on all subjects included in the population under consideration.

Summary statistics for continuous variables will include N, mean, standard deviation, minimum, lower quartile, median, upper quartile, maximum. Summary statistics for discrete variables will be presented in contingency tables and will include absolute and relative frequencies.

For categorical or binary variables, the number and percent of subject in each category will be presented. The p-values, if presented, will be two-sided unless otherwise specified, and 95% CIs will be provided as appropriate.

In general, efficacy data from the extension study period will be reported for clinical study report (CSR) and publication(s). Efficacy tables and figures corresponding to the hierarchy assessments (e.g. ASAS20/40 responder analysis) will be presented from Week 1 in the core study up till the end of reporting period in the extension trial.

No formal hypothesis testing will be done. Hence, the p-values and CIs provided should be considered as exploratory only.

Safety data from core and extension studies will be reported cumulatively for CSR and publication(s). Placebo safety data from core will be reported only in the listings. For subjects who switched from placebo to secukinumab in core, their data prior to switch will not be reported.

All listings will be presented by treatment groups. All listings but the listings of deaths, non-fatal serious adverse events and adverse events requiring treatment discontinuation will display the placebo group followed by the indication of responder or non responder.

5 Subjects and treatments

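### SAP 19.2.3 compares percent-scale confidence limits with a 0–1 proportion, so the truncation rule as printed replaces lower limits by the raw proportion

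*SAP*

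**What the plan says.** SAP Section 19.2.3 covers summaries of binary and categorical data. Where intervals are given, "CIs will be derived as well based on the score method including continuity correction". The section then sets out three things in sequence.

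- p is introduced "as estimated crude incidence (number of subjects with event / n", with q = 1 − p. It therefore lies between 0 and 1.
- L is 100 times the larger of 0 and the lower score expression. U is 100 times the smaller of 1 and the upper score expression. Both limits therefore lie between 0 and 100.
- A truncation rule follows: "In addition, if $L > p$ then $L = p$ and if $U < p$ then $U = p".

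A Clopper-Pearson interval is allowed as an alternative, but "the CI derived via the score method including continuity correction will be the default in safety analyses". The confidence level comes from SAP Section 4 (Data presentation): "95% CIs will be provided as appropriate".

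**The concern.** The truncation sentence compares a percentage with a proportion and then substitutes one for the other. Nothing in the section rescales p or says that the rule is applied before the multiplication by 100. A lower limit in percent will nearly always exceed a proportion, so the rule would overwrite lower limits that need no correction. An upper limit in percent will not fall below a proportion, so the upper half of the rule would do nothing.

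The interval is widely used. It is the safety default. SAP Section 16.1 sends the reader to the appendix for the intervals on crude adverse-event incidence; it cites a Section 19.3.3 that the SAP text does not contain, and 19.2.3 is where the binomial method is found. SAP Sections 13.2 and 14.1 promise 95% intervals for observed ASAS20 and ASAS40 proportions without naming a method, and 19.2.3 is the only method the SAP states for observed binary data. With no formal hypothesis test, these intervals are the main statement of uncertainty in the study.

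**Working it through.** The documents print no worked interval, so there is no figure of theirs to reproduce.

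**Inputs**
- Formulas for L and U, and the truncation rule: SAP 19.2.3.
- Two-sided 95% level, z = 1.96, z² = 3.8415: SAP Section 4.
- n = 300 as a round value inside the expected extension size, "which is equivalent to about 279 to 316 subjects" (SAP Section 18).
- n = 372 as an assumed core-study size. The documents do not state it; it is implied by 279 / 0.75 = 372 (and 316 / 0.85 = 371.8).

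**Step 1: are the base formulas sound?** Before the factor 100, with p a proportion:

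- lower = [2np + z² − 1 − z√(z² − 2 − 1/n + 4p(nq + 1))] / [2(n + z²)]
- upper = [2np + z² + 1 + z√(z² + 2 − 1/n + 4p(nq − 1))] / [2(n + z²)]

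For 180/300 (p = 0.60, nq = 120), the denominator is 2 × 303.8415 = 607.683.

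- lower = [360 + 3.8415 − 1 − 1.96 × √(3.8415 − 2 − 0.0033 + 2.4 × 121)] / 607.683 = (362.84 − 33.51) / 607.683 = 0.5420
- upper = [360 + 3.8415 + 1 + 1.96 × √(3.8415 + 2 − 0.0033 + 2.4 × 119)] / 607.683 = (364.84 + 33.46) / 607.683 = 0.6554

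Solving the continuity-corrected score equations numerically gives the same limits, here and at 81/263 and 1/300. The base formulas are correct.

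**Step 2: why a truncation rule is needed.** At the extremes the formulas overshoot the estimate. At 0/300 the lower limit is 0.03%, above an estimate of 0%. At 300/300 the upper limit is 99.97%, below an estimate of 100%.

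**Step 3: the rule as printed, and on one scale.** The printed rule compares L and U (percent) with p. The one-scale rule compares them with 100p.

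| Events / n | p | L, U before the rule (%) | L, U by the printed rule | L, U on one scale (%) |
|---|---|---|---|---|
| 0/300 | 0 | 0.03, 1.58 | 0, 1.58 | 0, 1.58 |
| 1/300 | 0.0033 | 0.017, 2.14 | 0.0033, 2.14 | 0.017, 2.14 |
| 5/372 | 0.013 | 0.50, 3.29 | 0.013, 3.29 | 0.50, 3.29 |
| 15/300 | 0.05 | 2.93, 8.29 | 0.05, 8.29 | 2.93, 8.29 |
| 60/100 | 0.60 | 49.70, 69.52 | 0.60, 69.52 | 49.70, 69.52 |
| 180/300 | 0.60 | 54.20, 65.54 | 0.60, 65.54 | 54.20, 65.54 |
| 300/300 | 1.00 | 98.42, 99.97 | 1.00, 99.97 | 98.42, 100 |

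**Step 4: how general is this?** Every count from 0 to n was evaluated at n = 5, 10, 20, 50, 100, 279, 300, 316 and 372.

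- Printed rule: the lower overwrite fires at every count (for example 301 of 301 at n = 300), and only x = 0 ends with the right lower limit. The upper overwrite never fires.
- One-scale rule: the lower overwrite fires only at x = 0 and the upper only at x = n, for every n.

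**The case against.** The strongest reply is that this is a notational slip with an obvious intent. On one scale the rule corrects exactly the two edge cases, and the section names a standard interval and cites its source. The SAS code in SAP 19.2.4 requests a continuity-corrected Wilson interval directly. A programmer who holds p and the limits on the same scale, or who uses that procedure option, would get correct results. The documents do not show which program will produce these tables. For common events a literal implementation would give an interval such as 0.6 to 65.5 around 60%, which someone would probably notice.

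The reach also has limits. The score interval is stated as the default only for safety; its use for observed ASAS20 and ASAS40 is an inference. The pooled multiple-imputation limits come from the logit scale and are unaffected, as are the exposure-adjusted rates in SAP 19.2.5. SAP Section 4 calls the intervals exploratory, so no decision rule depends on them.

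All of this stands as an argument about weight, but none of it reconciles the scales in 19.2.3. The safeguard of visible absurdity is weaker for rare events: at 1/300, limits of 0.0033 and 0.017 both print as 0.0 to one decimal, although the absolute difference is then trivial. At x = n the failure would be an upper limit of 99.97% beside an estimate of 100%, which is easy to overlook.

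**Conclusion.** Wrong as written, and minor. Followed literally, the rule replaces the lower limit by the raw proportion at every count and every n tried, and disables the correction of the upper limit at x = n. The damage to the lower limit grows with the event rate: 2.93% becomes 0.05 at 15/300, and 54.20% becomes 0.60 at 180/300.

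The conclusion rests only on the printed definitions and the 95% level; the values of n are illustrations, and 372 is back-calculated. Whether any reported table would be wrong depends on the program used, which the documents do not show.

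**What to change.** Replace the truncation sentence in SAP 19.2.3 with: if L > 100p then L = 100p, and if U < 100p then U = 100p. Equivalently, define L and U without the factor 100, apply the existing rule on the proportion scale, and multiply by 100 last. Do not simply delete the sentence, because the limits at 0 and n events do need it.

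The cost is a one-line SAP correction, plus a check that the table program gives 0 to 1.58% at 0/300, 54.20% to 65.54% at 180/300 and 98.42% to 100% at 300/300. Design, sample size and study conduct do not change.
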